9.2.2 Causality

The assessment of relationship of adverse events to the intervention is a clinical decision based on all available information at the time of the completion of the case report form.

If a differentiated causality assessment which includes other factors in the trial is deemed appropriate, please add/amend the following wording to specify:

It is of particular importance in this trial to capture events related to the procedure (Cognitive Stimulation Therapy) (refer to section 9.17 for reporting requirements). The assessment of relationship of an adverse event to this/these additional safety issue(s) will also be carried out as part of the trial.

The differentiated causality assessments will be captured in the trial specific CRF or SAE form (amend as required).

The following categories will be used to define the causality of the adverse event:

Category	Definition
Definitely:	There is clear evidence to suggest a causal relationship, and other possible contributing factors can be ruled out.
Probably:	There is evidence to suggest a causal relationship, and the influence of other factors is unlikely
Possibly	There is some evidence to suggest a causal relationship (e.g. the event occurred within a reasonable time after administration of the trial intervention). However, the influence of other factors may have contributed to the event (e.g. the participant's clinical condition, other concomitant events).
Unlikely	There is little evidence to suggest there is a causal relationship (e.g. the event did not occur within a reasonable time after administration of the trial intervention). There is another reasonable explanation for the event (e.g. the participant's clinical condition, other concomitant treatments).
Not related	There is no evidence of any causal relationship.
Not Assessable	Unable to assess on information available.

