3.1 Assessment and Management of Risk

There will be no invasive tests or procedures that will be included above standard care. All the assessments will be based on standardised questionnaires. The intervention is not invasive.

The table below summarise the risks and mitigations of all test above standard care that are being performed in a table:

Intervention	Potential risk	Risk Management
Individual Cognitive Stimulation Therapy	Distress to participants	If participants are distressed by activities, the session should be terminated.
Administration of cognitive tests	Distress to participants	If participants are distressed, the session should be terminated.

4 Objectives

Primary:

To adapt and modify a manualised individual Cognitive stimulation (iCST) intervention for people with intellectual disabilities.

Secondary:

- 1. To carry out a feasibility randomised controlled trial to determine the tolerability and acceptability of the intervention (iCST) by examining the number of eligible participants, willingness of clinicians to recruit participants, willingness of participants to be randomised, appropriateness of outcome measures, drop-out rates, adherence to the intervention and acceptability of the intervention.
- 2. To determine the standard deviation and mean for the primary outcome measure (improvement in cognition in individuals with dementia and intellectual disability), which will be used to determine the sample size for a larger trial.

5 Trial design

The initial phase will involve the adaptation of the intervention and development of the iCST manual for people with intellectual disabilities and dementia.

1. Adaptation of the intervention (6 months in total)

The intervention will be modified according to the Medical Research Council guidelines on developing complex interventions (17). We will follow a similar procedure to that employed by the UCL group in developing the intervention and manual for iCST (18) and also their guidelines for adapting CST in other cultures (19).

Stage 1: focus groups and interviews (month 0-3)

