- 1. Care giving burden in both paid and informal carers will be assessed using the Care Giving Burden Scale (25). Carers are asked if the individual requires assistance in a range of areas, whether they have provided assistance in the last month and whether providing assistance has been stressful. There are three domains and each has a maximum score of 15.
- 2. The competence to look after someone with dementia will be assessed using the Sense of Competence in Dementia Care Staff (SCIDS) Scale. This is a 17 item scale with four subscales (professionalism, Building relationships, Care challenges and sustaining Personhood. The maximum score is 68, with higher scores indicating more competence (26). Although this questionnaire was developed for care staff, the questions may also be relevant for family members. Minor modifications to the questions will need to be made to ensure that it is appropriate for use in both groups.
- 3. The presence of an anxiety or depressive disorder will be assessed using the Hospital Anxiety and Depression Scale (HADS) (27).

The baseline and subsequent assessments will take up to 90 minutes to complete with the individual with dementia and up to two hours to complete with the carer.

All pre-treatment procedures will be carried out as specified in the schedule of assessments (appendix 1).

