9.4 Procedures for recording and reporting Serious Adverse Events

All serious adverse events will be recorded in the medical records and the CRF, and the sponsor's AE log. The AE log of SAEs will be reported to the sponsor at least once or twice per year.

All SAEs (except those specified in section 9.5 as not requiring reporting to the Sponsor) must be recorded on a serious adverse event (SAE) form. The CI/PI or designated individual will complete the sponsor's SAE form and the form will be preferably emailed to the Sponsor within 5 working days of becoming aware of the event. The Chief or Principal Investigator will respond to any SAE queries raised by the sponsor as soon as possible.

Where the event is unexpected and thought to be related to the intervention, this must be reported by the Investigator to the Health Research Authority within 15 days.

Completed SAE forms must be sent within 5 working days of becoming aware of the event to the Sponsor

Email forms to [contact]

Managing serious adverse events in a multi-site trial (if applicable)

[figure not shown]
Serious Adverse Events will need to be reported by the PI to the CI within 48 hours. The CI will review the report first before submitting it to the sponsors within 24 hours. Safety information will be disseminated to all the PIs at the participating sites by the CI.

SAEs will be reported to the sponsor until the end of the trial.

Participants must be followed up until clinical recovery is complete and laboratory results have returned to normal or baseline values, or until the event has stabilised. Follow-up should continue after completion of protocol treatment.

Follow-up SAE forms (clearly marked as follow-up) should be completed and emailed to the JRO as further information becomes available.

Flow Chart for SAE reporting (this simple flow chart is for single site trial, please amend in line with trial specific requirements)

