Appendix 1 - Schedule of assessments

	Screening (pre- treatment assessment)	Intervention phase			Final visit	Optional	
Visit No:	1	2	3	4	5	6	7
		Week 1	Week 5	Week 11	Week 15	Week 20	
Window of flexibility for timing of visits:			e.g.+/- 7 days	E.g+/- 7 days		e.g.+/- 7 days	
Informed Consent	x						
Medical History	Х						
Eligibility confirmation (ICD- 10 criteria)	х						
CAMCOG-DS	х			х		х	
Memory for Objects Test	х			X		x	
CSDS	х			X		x	
ADCS-ADL	x			X		x	
QOL-AD	x			X		x	
Care giver burden scale	x			х		x	
HADS	x			х		x	
SCIDS Scale	х						
Training for carers		Х					
Treatment adherence/monitoring visit			Х		х		
Trial evaluation questionnaire						х	
Semi-structured interview							Х
Randomisation	Х						
Adverse Events review	X	X		X		X	
Concomitant Medication review	late version 1 (3	0/11/2015) X		х		х

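### Causality is rated only against iCST, although section 3.1 names cognitive testing as a second source of distress; this leaves a narrow gap in expedited reporting and makes related-event ratings hard to compare between arms

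*Protocol*

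**What the plan says.** The risk table in Protocol section 3.1 has two rows. One is iCST; the other is "Administration of cognitive tests". Both carry the same risk, participant distress, and both are managed by ending the session.

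Section 9.2.2 sets the causality question: "The assessment of relationship of adverse events to the intervention is a clinical decision". It then keeps an instruction from the protocol template: "If a differentiated causality assessment which includes other factors in the trial is deemed appropriate, please add/amend the following wording to specify". The text entered under that instruction is "It is of particular importance in this trial to capture events related to the procedure (Cognitive Stimulation Therapy", followed by a pointer to section 9.17. Section 9 ends at 9.10. The worked example under the category Possibly is also tied to iCST: "the event occurred within a reasonable time after administration of the trial intervention".

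Section 9.4 makes one reporting route depend on relatedness: "Where the event is unexpected and thought to be related to the intervention, this must be reported by the Investigator", with the Health Research Authority as recipient and a limit of 15 days.

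Testing is a sizeable exposure and is the same in both arms. Section 8.1 says: "The baseline and subsequent assessments will take up to 90 minutes to complete with the individual with dementia". Sections 8.1 and 8.4 place assessments at baseline, mid-point and end of intervention. Appendix 1 has a row "Adverse Events review" that is already marked at the screening visit, before any iCST.

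**The concern.** The protocol names two things it does to participants that may upset them, and asks a causality question about only one. The place meant for the second was filled in with the first.

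Two consequences follow. The first concerns reporting: a relatedness trigger worded for the intervention alone does not cover harm from the rest of the trial's procedures. The second concerns interpretation. Tolerability of iCST is a secondary objective in section 4, and so is whether the outcome measures are suitable. With a single causality question, some distress caused by testing may be attributed to iCST in the arm that receives it, while the same distress in a control has no comparable label. A reader of related-event counts could then take part of the burden of testing for a burden of iCST. The test battery, which a larger trial might reuse, would get no causality rating of its own.

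**Working it through.** The protocol states no adverse event rate and no figure to reproduce. The check is a comparison of sections, with a count of planned sessions to show where the problem can arise.

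**Step 1. Hazards named against hazards rated**

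| Hazard in 3.1 | Causality question in 9.2.2 | Within the 15-day trigger in 9.4 |
|---|---|---|
| iCST | Yes, in the opening sentence and again in the differentiated assessment | Yes, if unexpected |
| Cognitive tests | None stated | No |

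The differentiated assessment adds nothing, because the factor entered there is the intervention itself.

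**Step 2. The same test-related event under the categories as written**

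- *Baseline, either arm.* No iCST has been given. The plausible ratings are Unlikely, Not related or Not Assessable.
- *Follow-up, control arm.* The same three ratings, for the same reason.
- *Follow-up, iCST arm.* Possibly is also open. That category allows other contributing factors and uses timing after the intervention as its example, and with two sessions a week for 20 weeks an assessment usually falls close to a session.

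The arms therefore differ in the ratings available at follow-up even if testing causes exactly the same distress in each.

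**Step 3. Where the imbalance can arise**

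Inputs: 20 dyads per arm (sections 5 and 11.5) and two follow-up assessments (section 8.4).

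- Follow-up sessions per arm: 20 × 2 = 40 planned, before any dropout.
- Baseline sessions: 20 + 20 = 40. These precede randomisation and cannot create a difference between arms.

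The unequal rating thus concerns at most 40 planned sessions in the iCST arm set against 40 in controls. How many would produce a recordable event is not stated and cannot be derived from the protocol.

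**Step 4. What is caught whatever the cause**

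- Section 9.3 records every adverse event in the CRF.
- Section 9.4 sends every serious adverse event to the sponsor, and section 9.5 exempts none.
- Section 13.1 has the Trial Management Group review serious adverse events.

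Only the 15-day route depends on relatedness. What falls outside it is an event that is serious, unexpected and caused by the assessments.

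**The case against.** The strongest reply is that little is lost. Recording and sponsor reporting do not depend on cause. The only testing risk named is distress, which would seldom meet the seriousness definition in section 9.1. Section 9.2.3 already says that taking part may cause distress, so it would probably be classed as expected and would miss the 15-day route even if the trigger were widened. The burden of testing is also examined elsewhere: section 8.4 has an end-of-study questionnaire and interviews covering study procedures, and section 11.6.1 tracks completion of each assessment. The CRF and SAE form are not at hand and may carry a further field. Finally, the tolerability objective concerns iCST, and the protocol specifies no comparison of related events between arms.

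Most of this stands, and it is why the point is small. Three things survive it. Recording an event does not supply the missing attribution. The footnote to section 9.2.3 treats listed events that are more frequent or more severe than previously reported as unexpected, so a serious reaction to testing could be unexpected and still miss the trigger on the relatedness wording alone. And if tolerability of iCST is the objective, separating its effects from those of testing serves that objective.

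A reader might infer that harm from the assessments is coded as unrelated in both arms and so disappears. The documents do not support that. In the iCST arm such an event can be rated Possibly, elsewhere more than one rating is open, including Not Assessable, and the event is recorded in every case.

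**Conclusion.** The point holds in a limited form. Section 9.2.2 leaves the second hazard of section 3.1 without a causality rating, and section 9.4 words its only relatedness-dependent route for the intervention alone. Two consequences follow:

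- a serious, unexpected event caused by the assessments lies outside the 15-day HRA trigger;
- test-related events at follow-up can be rated differently by arm, so related-event counts would not be comparable and could lean against iCST.

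This assumes that the protocol is followed as written and that the forms add no causality field for assessments. The second consequence matters only if related events are tabulated by arm. No number of misattributed events can be given, since any rate would be a guess. Neither loss of safety data nor a large bias should be inferred. Priority is low, but the paragraph needs editing in any case, because it still holds template instructions and a dead cross-reference.

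**What to change.** In section 9.2.2:

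- name the trial assessments (cognitive tests and questionnaires) as the second factor in the differentiated assessment, in place of Cognitive Stimulation Therapy;
- state that each adverse event gets two ratings, one against iCST and one against the assessments, in both arms and from baseline;
- delete the leftover template instructions and correct or remove the reference to section 9.17.

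In section 9.4, change the wording of the trigger to *related to the intervention or to any trial procedure*.

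The cost is one extra field on the CRF and SAE form and the wording changes above. The drawback is that a few more events may be labelled as related to the trial.

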9.2.3 Expectedness

Category	Definition
Expected	An adverse event which is consistent with the information about the intervention listed in the SPC, manual of Operation (amend as appropriate) or clearly defined in this protocol.
Unexpected	An adverse event which is not consistent with the information about the intervention listed in the SPC, manual of Operation (amend as appropriate)* or clearly defined in this protocol.

^{*} This includes listed events that are more frequently reported or more severe than previously reported.

There are no known adverse effects of Cognitive Stimulation Therapy. However, taking part may possibly cause distress/ inconvenience for some participants with dementia

9.3 Recording adverse events

All adverse events will be recorded with clinical symptoms and accompanied with a simple, brief description of the event, including dates as appropriate.

All adverse events will be recorded in the CRF until the participant completes the trial.

9.4 Procedures for recording and reporting Serious Adverse Events

All serious adverse events will be recorded in the medical records and the CRF, and the sponsor's AE log. The AE log of SAEs will be reported to the sponsor at least once or twice per year.

All SAEs (except those specified in section 9.5 as not requiring reporting to the Sponsor) must be recorded on a serious adverse event (SAE) form. The CI/PI or designated individual will complete the sponsor's SAE form and the form will be preferably emailed to the Sponsor within 5 working days of becoming aware of the event. The Chief or Principal Investigator will respond to any SAE queries raised by the sponsor as soon as possible.

Where the event is unexpected and thought to be related to the intervention, this must be reported by the Investigator to the Health Research Authority within 15 days.

Completed SAE forms must be sent within 5 working days of becoming aware of the event to the Sponsor

Email forms to [contact]

Managing serious adverse events in a multi-site trial (if applicable)

[figure not shown]
Serious Adverse Events will need to be reported by the PI to the CI within 48 hours. The CI will review the report first before submitting it to the sponsors within 24 hours. Safety information will be disseminated to all the PIs at the participating sites by the CI.

SAEs will be reported to the sponsor until the end of the trial.

Participants must be followed up until clinical recovery is complete and laboratory results have returned to normal or baseline values, or until the event has stabilised. Follow-up should continue after completion of protocol treatment.

Follow-up SAE forms (clearly marked as follow-up) should be completed and emailed to the JRO as further information becomes available.

Flow Chart for SAE reporting (this simple flow chart is for single site trial, please amend in line with trial specific requirements)

9.5 Serious Adverse Events that do not require reporting (if applicable)

Not applicable

9.6 Unblinding (if applicable)

This is not relevant as the participants will be aware of the whether they are receiving the intervention. The research assistant administering the questionnaires will be blind to the treatment group.

9.7 Reporting Urgent Safety Measures

If any urgent safety measures are taken the CI/ PI shall immediately and in any event no later than 3 days from the date the measures are taken, give written notice to the relevant REC and Sponsor of the measures taken and the circumstances giving rise to those measures.

9.8 Notification of reportable protocol violations

A reportable protocol violation is a breach which is likely to effect to a significant degree:

- (a) the safety or physical or mental integrity of the participants of the trial; or
- (b) the scientific value of the trial.

The sponsor will be notified immediately of any case where the above definition applies during the trial conduct phase.

9.9 Reporting incidents involving a medical device(s) (if applicable)

Not applicable

9.10 Trust Incidents and Near Misses

An incident or near miss is any unintended or unexpected event that could have or did lead to harm, loss or damage that contains one or more of the following components:

- a. It is an accident or other incident which results in injury or ill health.
- b. It is contrary to specified or expected standard of patient care or service.
- c. It places patients, staff members, visitors, contractors or members of the public at unnecessary risk.
- d. It puts the Trust in an adverse position with potential loss of reputation.
- e. It puts Trust property or assets in an adverse position or at risk.

Incidents and near misses must be reported to the Trust through DATIX as soon as the individual becomes aware of them.

A reportable incident is any unintended or unexpected event that could have or did lead to harm, loss or damage that contains one or more of the following components:

- a) It is an accident or other incident which results in injury or ill health.
- b) It is contrary to specified or expected standard of patient care or service.
- c) It places patients, staff members, visitors, contractors or members of the public at unnecessary risk.
- d) It puts the Trust in an adverse position with potential loss of reputation.
- e) It puts Trust property or assets in an adverse position or at risk of loss or damage.

10 Data management

10.1 Confidentiality

All data will be handled in accordance with the UK Data Protection Act 1998.

The Case Report Forms (CRFs) will not bear the participant's name or other personal identifiable data. The participant's initials, date of birth and trial identification number, will be used for identification and this will be clearly explained to the patient in the Patient information sheet. Patient consent for this will be sought.

10.2 Data collection tools and source document identification

Data will be collected from sites on trial specific case report forms (CRFs) or data collection tools such as electronic CRFs.

Source data are contained in source documents and must be accurately transcribed on to the CRF. Examples of source documents are medical records which include laboratory and other clinical reports etc.

A source document list will be implemented prior to the start of the trial to identify:

- which data is to be recorded directly onto the CRF;
- which data is recorded firstly into source documents, such as medical notes, and then transcribed into the CRF; and
- which data is not to be recorded in the CRF but only recorded in source documents, e.g. participant questionnaires.

It is the responsibility of the investigator to ensure the accuracy of all data entered in the CRFs. The delegation log will identify all those personnel with responsibilities for data collection and handling, including those who have access to the trial database.

10.3 Completing Case Report Forms

All CRFs must be completed and signed by staff that are listed on the site staff delegation log and authorised by the CI/ PI to perform this duty. The CI/PI is responsible for the accuracy of all data reported in the CRF.

Once completed the original CRFs must be sent to the research team at UCL (Division of Psychiatry) and a copy kept at site. The CRFs must be returned within two weeks of the participant visit. Source data verification of a CRF page should be completed and all data queries answered prior to submission where possible.

10.4 Data handling

In the study, questionnaires (see section on pre-assessment and assessment measures) will be collected from patients in accordance with the patient consent form, patient information sheet and section 8 of this protocol.

The questionnaires will be appropriately sent to [name] (Division of Psychiatry, [name]) for statistical analysis and [name] will act as the data controller of such data for the study

[name] (Division of Psychiatry, [name]) will process, store and dispose of questionnaires in accordance with all applicable legal and regulatory requirements, including the Data Protection Act 1998 and any amendments thereto. Patient data will be stored centrally at in a locked filing cabinet controlled by the Chief Investigator.

The questionnaires will not be transferred to any party not identified in this protocol and are not to be processed and/or transferred other than in accordance with the patients' consent.

11 Statistical Considerations

